Comparison of the Efficacy of Single and Double Puncture Arthrocentesis in Treatment of Temporomandibular Joint Disc Displacement Without Reduction

Date: 20/03/2020

This document contains study design and statistical analysis plan of the study entitled "Comparison of the Efficacy of Single and Double Puncture Arthrocentesis in Treatment of Temporomandibular Joint Disc Displacement Without Reduction".

Study Design:

This is a two-armed, randomized, parallel interventional clinical study enrolling 36 patients with temporomandibular joint disc displacement without reduction (DDwoR).

*Eligibility:**Inclusion Criteria:*

- Clinical diagnosis of Temporomandibular joint (TMJ) disc displacement without reduction.
- Restricted mouth opening

Exclusion criteria:

- History of systemic disease effecting TMJ.
- History of previous TMJ surgery

Patients were grouped according to the treatment they received: Single Puncture Arthrocentesis as group SPA, Double Puncture Arthrocentesis as DPA.

Double puncture arthrocentesis technique:

Posterior puncture method was used as described by Alkan and Etoz for DPA. A straight line was drawn with a marker pen along the skin from the middle portion of the auricular tragus to the lateral chantus. The first puncture point was marked 10 mm anterior and 2 mm inferior to the tragus and the second 7 mm anterior and 2 mm inferior to the tragus. After local anesthesia, upper joint cavity was irrigated with 200 mL of Lactated Ringer's (RL) solution by inserting two 21- gauge needle. At the end of the procedure, after withdrawn of one of the needles, 1 mL of sodium hyaluronate (SH) was injected into the upper TMJ compartment through the other needle.

Single Puncture Arthrocentesis Technique:

SPA was performed with one needle (SPA Type-1 according to Senturk and Cambazoglu). The first reference point in DPA was used as the needle entry point fort he SPA. With this technique, the inflow and outflow of solution were provided through the same cannula and lumen of one 21-gauge needle as described by Guarda-Nardini et al. The joint was irrigated with 200 mL of RL solution under high pressure. At the end of the procedure 1 mL of SH was injected through

the needle

Outcome measures:

1. The Rate of Pain on Function (PoF) assessed by Numerical pain Scale (NRS)

Patients rated their pain on function (pain during chewing or speaking etc.) on a Numeric Rating Scale (NRS) (0–10 where 0 is no pain and 10 is the worst pain imaginable).

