Patients were evaluated at preoperatively and postoperatively 1st week, 1st month, 3rd month, 6th month.

2. The measurement of pain-free maximum mouth opening (MMO) in millimeters:

Pain-free MMO was measured as the distance between the incisal edges of the upper and lower incisors by a caliper while patient's mouth is open as possible without any assistance and without pain in masseter muscle. Three measurements were performed, and their average is recorded. Patients were evaluated at preoperatively and postoperatively 1st week, 1st month, 3rd month, 6th month.

3. The rate of pain at rest (PaR) assessed by Numerical pain Scale (NRS)

Patients rated their pain level at rest on a Numerical pain Scale (NRS)(0–10 where 0 is no pain and 10 is the worst pain imaginable). Patients were evaluated at preoperatively and postoperatively 1st week, 1st month, 3rd month, 6th month.

4. Measurement of Duration of the Procedure in Minutes.

Total time for arthrocentesis was noted at the end of the procedure.

Patients were evaluated at the end of the procedure

5. Measurement of the easiness of the procedure to the operator by using Visual Analog Scale (VAS):

The operator rated the degree of easiness of the procedure on a VAS as 0-very easy 10-very difficult to perform at the end of the procedure

6. The rate of treatment tolerability assessed by 5-point Likert-type scale:

The degree to which overt adverse effects and post operative complications (pain, feeling of pressure in TMJ area and disturbing sound) can be tolerated by the patient. Patients were asked to rate the tolerability on a 5 point scale as 0- lowest, 4-highest at operation day, 1st week, end of follow up period (6th month)

7. The rate of chewing efficiency by using Visual Analog Scale (VAS):

Patients rated the chewing efficiency on a VAS as 0-can only eat semi-liquid foods, 10-eat any solid-food. Patients were evaluated at preoperatively and postoperatively 1st week, 1st month, 3rd month, 6th month.

8. Rate of perceived effectiveness of the treatment by using 5-point Likert-type scale:

Patients rated the subjective treatment effectiveness on a 5-point scale as 0- lowest, 4 highest values at the end of the follow up period (6th month).

9. Measurement of Lateral Movement of the mandible towards the affected Temporomandibular joint (TMJ) in millimeters

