Lateral Movement of the mandible towards the affected Temporomandibular joint (LT) was measured as the distance between the midlines of the upper and lower incisors by a caliper while patient's mandible was shifted towards the affected TMJ. Three measurements were performed, and their average is recorded. Patients were evaluated at preoperatively and postoperatively 1st week, 1st month, 3rd month, 6th month.

10. Measurement of Lateral Movement of the mandible away from the affected Temporomandibular joint (TMJ) in millimeters

Lateral Movement of the mandible away from the affected Temporomandibular joint (LA) was measured as the distance between the midlines of the upper and lower incisors by a caliper while patient's mandible was shifted away from the affected TMJ. Three measurements were performed, and their average is recorded. Patients were evaluated at preoperatively and postoperatively 1st week, 1st month, 3rd month, 6th month.

11. Measurement of protrusive movement of the mandible in millimeters:

Protrusive movement of the mandible was measured as the distance in horizontal direction between the incisal edges of upper and lower incisors by a caliper when mandible moves forward. Patients were evaluated at preoperatively and postoperatively 1st week, 1st month, 3rd month, 6th month.

Statistical Analysis:

IBM SPSS 22 was used to analyze the data (IBM SPSS Statistics for Windows, Version 22.0. Armonk, NY: IBM Corp.). Descriptive statistics of the variables were presented as mean \pm standard deviation in statistical analysis. Normality of distribution for continuous variables was evaluated using the Kolmogorov-Smirnov test. Depending on whether the statistical hypotheses were fulfilled, either the Student's t-test or the Mann-Whitney U test was used to compare the independent continuous variables between the two groups, Wilcoxon signed rank test was used for intra-group evaluation of variables according to baseline such as PoF ve MMO. Statistical significance level was accepted as $p < 0.05$.

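### For the seven outcomes with a preoperative value, the planned SPA–DPA comparison states no use of that value, so precision may be lost; how much depends on a baseline–outcome correlation the documents do not give

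*Combined protocol and SAP*

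**What the plan says.** The Study Design section describes the trial thus: "This is a two-armed, randomized, parallel interventional clinical study enrolling 36 patients". It gives no allocation ratio and no sample-size calculation.

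Under Outcome measures, items 1, 2, 3, 7, 9, 10 and 11 (PoF, MMO, PaR, chewing efficiency, LT, LA, protrusion) share one schedule: "Patients were evaluated at preoperatively and postoperatively 1st week, 1st month, 3rd month, 6th month". The other four items (duration, ease for the operator, tolerability, perceived effectiveness) have no preoperative value and are not part of this point.

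The Statistical Analysis section gives one method for comparing the arms: a Student t-test or, where its assumptions fail, the "Mann-Whitney U test was used to compare the independent continuous variables between the two groups". It names no covariate, model or change score. The only sentence that mentions baseline concerns change within each arm: "Wilcoxon signed rank test was used for intra-group evaluation of variables according to baseline such as PoF ve MMO".

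**The concern.** The trial asks whether SPA and DPA differ. For seven outcomes it collects the preoperative value, often a useful predictor of the follow-up value. As described, the plan uses it only in a within-arm test, which shows whether each arm changed but cannot show whether the arms differ.

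With 36 patients the between-arm estimate is imprecise, so discarding a useful covariate could matter. The plan also does not say whether the variable compared between arms is the follow-up value or the change from baseline. The outcomes are defined as values recorded at visits, so the follow-up value is the natural reading, but change is not ruled out.

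No bias or inflated type I error is at stake. Under randomisation the unadjusted test keeps its unconditional 5% level. The question is how much precision is given up.

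**Working it through.** The documents state no power, effect size, SD or correlation, so there is no figure of the plan's own to reproduce.

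**Inputs.** From the documents: 36 patients, significance level 0.05, seven outcomes with a preoperative value. Assumed: 18 per arm, two-sided tests, approximately normal data, and a within-arm correlation r between baseline and follow-up of 0, 0.3, 0.5 or 0.7. Differences are in units of the follow-up SD.

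**Formulae.** Let f be the variance of the arm difference relative to the unadjusted comparison of follow-up values.

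- Unadjusted follow-up value: f = 1, df = 34.
- ANCOVA: f = (1 − r²)(1 + 1/(36 − 4)) = (1 − r²) × 1.03125, df = 33. The second factor is the finite-sample cost of estimating the slope.
- Change score: f = 1 + k² − 2rk, df = 34, where k = baseline SD / follow-up SD.

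Power at difference d comes from the noncentral t distribution with noncentrality d / √(f × 2/18). The 95% CI half-width is t(0.975, df) × √(f × 2/18). The unadjusted sample size giving the same variance as ANCOVA with 36 patients is 36/f.

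**Follow-up value against ANCOVA.** For example, at r = 0.5, f = 0.75 × 1.03125 = 0.773 and 36/0.773 = 46.5.

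| Analysis | f | Detectable at 80% power (SD) | Power at 0.8 SD | CI half-width (SD) | Equivalent unadjusted N |
|---|---|---|---|---|---|
| Follow-up value | 1 | 0.961 | 64.5% | 0.677 | 36 |
| ANCOVA, r 0 | 1.031 | 0.977 | 63.1% | 0.689 | 34.9 |
| ANCOVA, r 0.3 | 0.938 | 0.932 | 67.2% | 0.657 | 38.4 |
| ANCOVA, r 0.5 | 0.773 | 0.846 | 75.5% | 0.596 | 46.5 |
| ANCOVA, r 0.7 | 0.526 | 0.698 | 89.5% | 0.492 | 68.4 |

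The detectable differences are equal at r of about 0.18; below that, ANCOVA is slightly worse.

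**Simulation check.** With normal data, a true difference of 0.961 SD and 4,000 runs per value of r, ANCOVA had power 0.80, 0.83, 0.89 and 0.97 at r 0, 0.3, 0.5 and 0.7. The unadjusted t-test had 0.79 to 0.81 and Mann-Whitney 0.76 to 0.78.

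**Other sample sizes** (r 0.3/0.5/0.7). With 15 per arm: 1.060 SD unadjusted against 1.032/0.937/0.772 with ANCOVA. With a 16/20 split: 0.967 against 0.938/0.851/0.702.

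**If change from baseline were compared instead** (r 0.3/0.5/0.7):

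- k = 1: detectable difference 1.137/0.961/0.745 SD; power at 0.8 SD 50.4/64.5/85.3%.
- k = 1.25: 1.294/1.101/0.867 SD.
- k = 0.8: 1.035/0.881/0.693 SD.

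The change score beats ANCOVA only over a limited range of k. Its largest advantage, at k = r, is 0.015/0.014/0.011 SD. At r 0.3 and k = 1 it is worse by 1.137 − 0.932 = 0.205 SD.

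**Bounded 0–10 scores.** Normal theory flatters the pain and chewing scales, so integer scores cut off at 0 and 10 were simulated, with 40,000 runs per cell. The assumed latent baseline mean was 7 with SD 2, and the latent follow-up means of 1, 2.5 and 4 put 40%, 16% and 4% of reference-arm scores at zero. Linear ANCOVA kept a type I error of 4.9% to 5.1% in all nine cells. For a latent shift of 0.8 SD its power was 62.5–66.3% (r 0.3), 69.5–73.4% (r 0.5) and 81.9–86.8% (r 0.7); Mann-Whitney had 59.7–61.7%. Reruns that added the unadjusted t-test put it at about 60–65%. The part of the gain due to baseline itself is therefore about 2–3 percentage points at r 0.3, 9–10 at r 0.5 and 21–23 at r 0.7.

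**The case against.** The strongest reply is that this is a matter of efficiency, not error. The unadjusted test is valid, no stated power target is missed because none is stated, and the benefit rests entirely on an r that the documents do not supply. At r 0.3 the gain is small, and below about 0.18 it is a slight loss. Entry requires "Restricted mouth opening", which may narrow the spread of baseline MMO and lower r for that outcome. All of this stands, and it limits how strongly the point can be put. The trade is nevertheless lopsided: at r 0 the detectable difference rises by 0.977 − 0.961 = 0.016 SD, while at r 0.5 it falls by 0.961 − 0.846 = 0.115 SD.

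Second, the text does not exclude a comparison of changes, in which case baseline would be used. The MMO, LT and LA definitions say "Three measurements were performed, and their average is recorded", but that describes averaging caliper readings and does not settle which variable is analysed. This also stands. It does not remove the point, because a change score improves on ANCOVA by at most 0.015 SD at the r values examined and can be much worse, and because leaving the choice open is itself a gap.

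Third, adjusting at every visit means 7 × 4 = 28 models with no main outcome or visit named. That is true, but the unadjusted comparison at each visit would involve the same 28 tests, so adjustment adds none.

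Fourth, the section is in the past tense ("IBM SPSS 22 was used to analyze the data"), so data may already have been seen. The documents do not say. If so, the adjusted analysis is still informative but is no longer prespecified.

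**Conclusion.** The concern holds. For seven of the 11 outcomes the plan states no use of the preoperative value in comparing SPA with DPA. The cost is a possible loss of precision, not of validity. Relative to ANCOVA, the unadjusted comparison gives up little at r 0.3, a useful amount at r 0.5 and a large amount at r 0.7 (equivalent to about 38, 47 and 68 unadjusted patients against 36).

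These sizes rest on 18 per arm, two-sided testing and assumed correlations. On the 0–10 scales the power levels are somewhat lower, but the gain persists at r 0.5 and above. This is a worthwhile, nearly free improvement. Confidence in its size is moderate, because r is unknown and may differ between outcomes.

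**What to change.** Add to the Statistical Analysis section:

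> For PoF, PaR, MMO, chewing efficiency, LT, LA and protrusion, SPA and DPA are compared at each postoperative visit by linear ANCOVA of the recorded value on arm and the patient's own preoperative value. The adjusted SPA–DPA difference is reported with its 95% CI, in millimetres or scale points.

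Keep Mann-Whitney on the follow-up value as the named sensitivity analysis, with no data-driven switch of the main model, and present within-arm changes descriptively. This also settles whether the follow-up value or the change is analysed.

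The cost is SAP wording, one SPSS procedure, a residual check and one degree of freedom; no new data or visits are needed. The price if baseline proves uninformative is the r 0 row of the table. If outcome data have already been examined, report the adjusted analysis as added afterwards.

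### No primary outcome, visit or test order is named: if all 29 efficacy comparisons are tested at p < 0.05, the chance of a false significant difference is about 77% if they are independent and 39–67% under assumed moderate-to-strong correlation

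*Combined protocol and SAP*

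**What the plan says.** The title announces a "Comparison of the Efficacy of Single and Double Puncture Arthrocentesis". The Outcome measures section numbers its outcomes 1 to 11. None is labelled primary or secondary.

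Seven are efficacy measures on a common schedule ("Patients were evaluated at preoperatively and postoperatively 1st week, 1st month, 3rd month, 6th month"): pain on function (PoF), pain-free maximum mouth opening (MMO), pain at rest, chewing efficiency, lateral movement towards the affected joint, lateral movement away from it, and protrusion. Perceived effectiveness is rated once, "at the end of the follow up period (6th month").

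The other three are procedure duration ("Total time for arthrocentesis was noted at the end of the procedure"), operator ease ("The operator rated the degree of easiness of the procedure on a VAS") and tolerability ("The degree to which overt adverse effects and post operative complications", as the patient rates them).

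The Statistical Analysis section gives one between-arm rule, a t-test or Mann-Whitney test for continuous variables, and a within-arm Wilcoxon test against baseline. It closes with "Statistical significance level was accepted as" p < 0.05. The 36 patients are stated without a sample-size calculation, so no primary outcome can be inferred from one.

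**The concern.** The 5% level holds for each test taken alone. The efficacy question, however, is spread over many outcome-and-visit pairs, and the plan does not say which of them answers it. A significant result on any one pair could be presented as the finding on efficacy. The trial's main conclusion would then carry a false-positive risk well above 5%, and the plan gives a reader no basis for separating such a result from chance.

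**Working it through.** **Inputs from the document.** Per-test level 0.05 (Statistical Analysis); 36 patients in two arms (Study Design); outcomes and schedules (Outcome measures).

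**Assumptions.** Two-sided tests and 18 patients per arm, because neither sidedness nor the allocation ratio is stated. No correlations are given, so a range is used.

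**Count of between-arm efficacy tests**
- 7 repeated outcomes × 4 post-operative visits = 28.
- Plus perceived effectiveness at 6 months = 29. This falls to 28 if that 5-point rating is outside the rule for continuous variables.
- One visit per efficacy outcome: 7 + 1 = 8.
- Duration, operator ease and tolerability are left out: they are not efficacy measures, and equal efficacy would not make them null. Within-arm tests are left out because they do not compare the techniques.

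**Independent tests, no true difference: 1 − 0.95^k**
- k = 29: 1 − 0.95^29 = 0.774
- k = 28: 1 − 0.95^28 = 0.762
- k = 8: 1 − 0.95^8 = 0.337
- Expected false positives among 29: 29 × 0.05 = 1.45

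**Correlated tests.** Simulation of normal data under no true difference, with t-tests and 40,000 trials per row. The last column repeats the 29 tests with Mann-Whitney (20,000 trials).

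| Correlation within / between outcomes | 29 tests | 8 tests | 29 tests, Mann-Whitney |
|---|---|---|---|
| 0.5 / 0.2 | 0.675 | 0.320 | 0.688 |
| 0.7 / 0.3 | 0.577 | 0.302 | 0.601 |
| 0.8 / 0.4 | 0.498 | 0.282 | 0.520 |
| 0.8 / 0.5 | 0.449 | 0.258 | 0.476 |
| 0.8 / 0.6 | 0.391 | 0.226 | 0.414 |
| 0.9 / 0.7 | 0.303 | 0.198 | 0.323 |
| 0.8 / 0.8 | 0.260 | 0.158 | 0.286 |
| 0.9 / 0.9 | 0.177 | 0.124 | 0.196 |

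The first five rows are the moderate-to-strong range, 0.9 / 0.7 is very strong, and the last two are extreme. Mann-Whitney raises the figures by at most 3 percentage points.

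**Check of the remedy (chance of any false claim)**
- PoF, then MMO, each at 0.05, with Holm on the other 27 tests opened only if both are significant: 0.047–0.052 with no true difference, and 0.011–0.052 when PoF, or PoF and MMO, truly differ.
- The same without that gate, no true difference: 0.094–0.095 if independent, 0.082 at 0.7 / 0.3, 0.060 at 0.9 / 0.7. The gate is needed.
- Holm over all 29, no true difference: 0.011–0.047.

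**Power (noncentral t, 34 df)**
- 80% power at α = 0.05 needs a difference of 0.961 SD.
- 80% power at the first Holm step, 0.05/29 = 0.00172, needs 1.429 SD.
- Power for 0.961 SD at 0.00172 is 0.324.
- Simulated full Holm power for one comparison with a true 0.961 SD difference: 0.32–0.33 if only that comparison differs, 0.35–0.36 if four outcomes differ at all visits, 0.40–0.43 if all 29 differ.

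**The case against.** - **The plan never says every visit is tested.** True; 29 is the natural reading of the schedules, not a stated rule. The 8-test reading still gives 12–34%, and that assumes the visit is fixed beforehand, which the plan does not do.
- **The correlations are assumed.** This stands. The 39–67% band is illustrative: taking its lower edge at 0.9 / 0.7 instead of 0.8 / 0.6 would bring it to 30%. No row of the table approaches 5%.
- **77% is not an absolute ceiling.** Also correct. It is the independence value, and an upper bound for two-sided tests on jointly normal statistics. That should hold approximately here, but several outcomes are bounded ratings.
- **PoF and MMO are singled out.** They head the list and appear as examples for the within-arm test. Neither fact designates a primary between-arm comparison, and the visit would still be open.
- **A reader shown every result can count the tests and look for consistency.** This is fair, and the harm comes through selective emphasis. The plan does not commit to full reporting and leaves that emphasis free.
- **The methods are in the past tense, so naming a primary may come too late.** This is a real limit. It changes the remedy, not the defect, and for 36 patients an exploratory label may be the proportionate answer.

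**Conclusion.** The concern holds and must be fixed, because it bears on the trial's main conclusion. The absence of a primary outcome, visit, order or adjustment is plain from the text and needs no simulation. Its size depends on the reading. For 29 tests the false-positive chance is 77% if independent, about 39–67% under moderate-to-strong correlation, about 30% under very strong correlation, and 18–26% in the extreme case. For 8 tests the corresponding figures are 34%, 23–32%, 20% and 12–16%. One designated test would give 5%. All of this supposes no true efficacy difference on any comparison, and every figure other than the independence ones rests on the assumed correlations, normal data and 18 per arm.

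**What to change.** **If the arms have not been compared.** Name one primary comparison in the SAP, for example PoF at the 6th month (the first listed outcome, at the stated end of follow-up), two-sided at 0.05. Test MMO at the 6th month next, only if PoF is significant. The sponsor may put MMO first, since "Restricted mouth opening" is an entry criterion, but must fix the order beforehand. Report all other outcomes and visits as secondary, with between-arm differences, 95% confidence intervals and no significance claims. Alternatively, test them by Holm over a family listed in advance, opened only if both steps are significant. The cost is wording only; no new data are needed.

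**If the arms have been compared.** Label any primary designation post hoc and report every between-arm comparison made. Then either Holm-adjust across that whole family or call the results exploratory. A designation made now does not restore 5%. Holm over 29 tests raises the difference detectable with 80% power from 0.96 to 1.43 SD at its first step. Power for a 0.96 SD difference falls from 80% to about 32% at the least, or about 40–43% if all 29 comparisons differ by that amount.

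Either way, isolated significant results can no longer be presented as confirmed differences.
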